3.1 Analysis of primary composite PDC outcome

3.1.a Summary of modeling approach

We propose to calculate a composite PDC ratio of days covered for each subject and analyze it using a standard longitudinal model for monthly PDC values, with a linear mean model, and with robust standard error estimation and associated inference based on weighted Generalized Estimating Equations (GEE), e.g. Robins et al., 1995; Preisser et al., 2002. In more detail and with rationale:

Outcome distribution: Since data are in the form of a discrete proportion, our original proposal was based on Bernoulli/binomial models. However, treatment-blinded examination of a sample of outcome data showed that the binomial assumption will not apply due to spikes caused by common prescription lengths (e.g. 30 and 90 days), and strong overdispersion or equivalently lack of independence of daily outcome data over time. We considered alternative approaches such as Poisson with offset for number of observation days but similar challenges of spikes, overdispersion and lack of independence remain. Ultimately, with the large number of subjects available for analysis (~10,000) and the bounded distribution of PDC (between 0 and 1), central limit theorem arguments make standard linear modeling valid in this situation (e.g. Lumley et al., 2002), and robust inference methods described below provide additional assurance of valid inference even with heteroscedastic variance in the outcomes.

Missing and truncated follow-up: Missing data and truncated follow-up for PDC have occurred for several reasons. Patients with inpatient stays have medications supplied by the hospital and thus don't deplete their own supplies, so such days are omitted from both numerator and denominator of PDC. Other situations resulted in early termination of PDC calculation. Prescribed medications are sometimes terminated by providers, or patients may die during follow-up. Additionally, initial study procedures did not allow for collection of outcome data on patients who opted out, and while this was fixed early in the study a small percentage of early patients have shorter PDC observation. Finally, treatment delivery was disrupted by two external situations specific to health care systems, one involving a new VA messaging system that would confound delivery of Nudge treatment messages, and one involving gap identification for patients at UCHealth. In both cases, when the issue occurred our enrollment targets had been surpassed at each system. Delivery of Nudge treatments was stopped and collection of daily PDC outcome data was truncated. The disruptions due to these two exogenous events resulted in data that can be assumed missing completely at random (MCAR), however this is likely not true for the other cases of early termination of PDC observation. Further examination of the treatment-blinded outcome data showed an increasing trend over time from time zero in PDC during periods shortly after randomization, due to the initial gaps. This together with early termination could result in biased estimation.

Longitudinal models and GEE: To account for the situations of shortened PDC observation and possible resulting biases we will use a longitudinal model with PDC calculated for monthly intervals. We will use GEE with identity link and independence with unequal variances for the covariance structure. This approach provides robust and likely conservative (Hernán et al., 2002) estimation using empirical (sandwich) variance estimates, but is valid only for MCAR data. However, use of weighting can extend GEE to data missing at random (MAR). In this approach, observation-specific weights are equal to the inverse probability that the longitudinal value was observed. Probability of observation will be estimated by a logistic regression model for whether the value was observed (y/n), with covariates listed in section 3.1.c below. Weights greater than the 95th percentile of weights will be set to the 95th percentile weight. These methods can be implemented for example in SAS PROC GEE (Lin & Rodriguez, 2015) or R package wgeesel (Xu et al., 2018). We will use multiple imputation to impute missing covariate data. We will carry out the recommended sensitivity analyses to the MAR assumption using methods based on pattern mixture models and imputation, by assuming a range of

perturbations of imputed values and assessing differences in model conclusions (e.g. White et al., 2011; Fiero et al., 2017).

Treatment comparisons: Discussions with clinicians have indicated expressing results on a linear scale (PDC differences), as opposed to odds ratios or risk ratios, will be most appropriate for interpretation. This occurs naturally with the linear specification in 3.1.a and identity link in GEE. Estimation and inference will be carried out using the parameter estimates from the robust GEE estimation to construct expected PDC treatment differences. The estimand comparisons will be 12-month PDC, calculated by summing the 12 monthly longitudinal parameters, which incorporate the adjustments for early termination of some subjects using the weighted GEE approach. Primary hypotheses involve pairwise comparisons between each of the four study arms, and will be conducted using a multistage gatekeeper approach to account for the multiple treatment comparisons. In stage 1 of this approach, each of the three active intervention arms is compared with the control arm using significance level 0.05/3. In stage 2, if any of the three stage 1 tests is significant, the three pairwise comparisons among active intervention arms are tested with the Holm method using significance level (R/3)*(0.05/3), where R is the number of stage 1 tests that were significant (Dmetrienko et al., 2008).

3.1.b Defining composite PDC for multiple medications

There are 13 CV medication classes considered in this study, and the primary outcome is composite PDC across medications a patient is prescribed. There are several considerations in defining composite PDC, including which of a patient's medications to include in the composite PDC calculation, and calculation of composite PDC with differing lengths of follow-up for different medications.

Medications to include in composite PDC: We have considered three ways of selecting medications to include in the primary PDC outcome: PDC1) all medications on which a patient gapped at baseline, PDC2) all medications a patient ever gaps on, calculating PDC from the time of gap, and PDC3) all medications a patient was prescribed at baseline. Medications prescribed after the baseline gap and enrollment will not be included in any of these definitions of PDC, though they will be considered in secondary analyses. Each definition (1-3) has benefits and shortcomings. PDC1 is closest to a pure effect of the intervention, but exploratory analyses of pilot data have shown that many patients who gap in a medication and are randomized also gap in another medication shortly thereafter. Specifically, preliminary data indicate that ~16% of patients gap on an additional medication within 30 days of baseline and ~37% within 90 days. PDC1 will omit these other medications prescribed but not gapped on at baseline. PDC2 provides a similar estimate incorporating these later-gapped medications but excludes medications the patient may never gap on due to reminders for other medications. PDC3 provides an estimate of the overall effect of the interventions on medication patterns, incorporating indirect effects of reminders, but risks inflating PDC and diluting intervention effects by including medications the patient never gaps on. Our primary analyses will use PDC1, while PDC2 and PDC3 will be considered in secondary analyses.

Composite PDC with differing lengths of follow-up: In general, PDC is the sum of observation days covered divided by the sum of observation days. Due to variations from the planned 365 days of assessment, there are several ways of calculating composite PDC for multiple medications. Information on hospitalizations, and on medication changes and cancellations, will be available from the patient's electronic health record. Note that at-risk days is medication specific, as medications may change during the one-year assessment period. Our primary PDC calculation will be PDC-C1 = (sum of numerators of medication-specific PDCs) / (sum of denominators of medication-specific PDCs). This can also be viewed as a weighted sum of medication-specific PDCs with weights equal to the proportion of the 365 target days for which PDC was observed, and equally weights each day on each medication. PDC-C1 will be the outcome definition in the longitudinal models described in section 3.1.a. As a sensitivity

analysis we will also consider an alternate definition, PDC-C2 = average of medication-specific PDCs, which equally weights medications regardless of their length of observation. When all medications are observed for 365 days these definitions are equal. For the longitudinal analyses planned, these definitions will be applied within each longitudinal interval. We will carry out the recommended sensitivity analyses based on pattern mixture models, by assuming various values for difference in means between observed and unobserved data and assessing differences in model conclusions.

3.1.c Adjustment/propensity covariates

The linear weighted GEE model for PDC and the logistic model for propensity of observation will each contain terms for randomization stratification variables health care system (VA, Denver Health or CUHealth), number of CV medications prescribed at baseline (1-2 or 3+), calendar month of randomization; treatment arm, follow-up month from randomization in longitudinal analysis, and treatment by follow-up month interaction; patient demographics age, race, ethnicity, insurance status, and marital status; and comorbidity variables hypertension, hyperlipidemia, coronary artery disease, diabetes, atrial fibrillation, chronic heart failure, chronic kidney disease, cerebrovascular disease, prior myocardial infarction, prior revascularization, depression, PTSD, and substance abuse.

3.1.d Alternate measures of medication adherence

We will consider several alternate analyses for medication adherence.

Alternate definitions of PDC: Alternate definitions PDC2 and PDC3 and alternate composite PDC-C2 defined above will be analyzed using the same methods as for the primary definition PDC1-C1. These analyses will provide a better understanding of indirect effects of treatments, and of effects of treatments on all medications a patient is prescribed.

Sensitivity to inactive medications: Among medications gapping at baseline, we will repeat the primary analysis limiting our analyses to those medications that had at least one fill during the follow-up period. This will allow us to assess treatment effects among medications that are known to be active, removing medications that were cancelled but not indicated as such by the medical record.

Medication-specific adherence: We will calculate and analyze PDC for each medication individually, to allow analyses of heterogeneity of treatment effect (HTE) by drug class. Multiple comparisons will be adjusted for separately for each analysis using the gatekeeper approach described above.

Medication gaps: We will consider alternate ways of describing medication adherence behavior, including length of initial gap, time to subsequent gap, average length of gaps, and number of 7-day gaps.

3.1.e Secondary examinations of medication adherence

In secondary analyses we will examine several other questions related to medication adherence, including:

Predictors of medication gaps: We will examine predictors of patients having an initial gap of at least 7 days, using the initial pool of candidate patients, to identify types of patients or prescription characteristics for patients at highest risk for non-adherence. We will also examine predictors of subjects having a gap of at least 7 days while enrolled in the study.

Mechanism of treatment effects: We will carry out analyses examining mechanisms or mediators of treatment effect by considering direct responses to reminders, including time from first reminder to refill, and measures of patient engagement, e.g. number of patient text responses to reminders (intensive text and chatbot arms only).

Heterogeneity of treatment effect: We will carry out analyses examining HTE, specifically i) HTE between the three health care systems, and ii) HTE for patient characteristics or subgroups

of particular interest. HTE analyses will be carried out using interactions as recommended in Kent et al., 2010 ²³ and will be considered exploratory.

3.1.f Original power analysis

We first estimate sample size required to achieve 80% power for the desired change in the primary outcome, then used current data to show we will be able to achieve this sample size.

Power and sample size: Required sample size was estimated for the primary outcome PDC during the 12 months following randomization. Preliminary data from the VA were used for these estimates. We made the following assumptions: a) Significance using two-sided level 0.05 tests, b) Power at least 80%; c) Difference between treatments in PDC of 10 percentage points; d) Bonferroni adjustment for the 6 pairwise comparisons among the 4 study arms, resulting in adjusted level 0.05/6 (a conservative alternative of the sequential gatekeeper approach to be used in the final analysis as described above, to simplify the calculation of power); e) Analysis stratified by health care system; and f) Within-system and within-treatment residual standard deviation of 12 month PDC equal to 0.22 (mean 0.732), obtained by analysis of 2,859 veterans during the period 01/01/2017 – 12/31/2017 who were prescribed the medications of interest in this study. The large SD is due to a highly left-skewed PDC distribution. (We base sample size estimation on t-tests rather than the proposed binomial models since we do not have estimates of quantities needed to carry out power simulations. We may be able to obtain data for the PDC outcome for a set of baseline patients, in which case we will consider a refined power analysis.) Using these assumptions and estimates, and comparing any two treatments using a linear model with the above residual standard deviation of PDC, we estimate using sample size functions in R that we will need N=119 subjects per treatment arm, total across the three health care systems, for a total of 476 subjects to be randomized across the three health care systems.

Available sample sizes: We obtained data from each of the three health care systems on the number of patients at the seventeen specific clinics (VA, 4 clinics; UCHealth, 5 clinics; DH 8 clinics) to be included in this study. Figure 1, which we believe to present conservative estimates of enrollment, shows estimated numbers of patients with CVD conditions and prescribed CVD medications across the 3 HCS. Patients will be sent a letter with the opportunity to opt-out. In addition, care providers will be provided lists of their patients who are potentially eligible for the study to see if there are patients that they feel should not be included in the study. Assuming that 75% of patients have a gap, another 15% of patients opt-out of the study following randomization, and 10% of patients do not have usable outcome data, we expect to have usable outcome data for about 7,740 patients across the four study arms.

Planned enrollment: In the patient accrual proposal sent to NHLBI (March 20, 2019), we proposed to enroll 5,000 patients which is a conservative estimate in case the number of patients opting out is higher than in the pilot or the number of patients with 7-day gaps is lower than estimated. Even with this conservative estimate, we expect to have ample subjects (nearly ten times as many as needed) to achieve the necessary power for the primary analysis of PDC. Additional subjects will provide power for secondary analyses, and for analyses of secondary outcomes.

Achieved sample sizes 3/2023

We surpassed our overall enrollment goal of 5,000 patients, enrolling 1,235 patients the VA, 7,266 patients at Denver Health, and 1,000 patients at UCHealth.

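### The observation model behind the GEE weights contains no PDC history, so the primary analysis holds under a narrower missing-data assumption than the MAR the SAP claims

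*Combined protocol and SAP*

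**What the plan says.** SAP 3.1.a (Missing and truncated follow-up) names several reasons for shortened PDC observation: inpatient days, provider cancellation, death, early opt-outs, and the VA and UCHealth disruptions. It treats the two disruptions as MCAR, but "however this is likely not true for the other cases of early termination of PDC observation". It adds that PDC rises soon after randomization, so early termination could bias estimation.

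SAP 3.1.a (Longitudinal models and GEE) specifies monthly PDC, an identity link and an independence working covariance. It states that this is valid only under MCAR and that weighting can extend it to MAR. The weights are inverse probabilities from a "logistic regression model for whether the value was observed (y/n), with covariates listed in section 3.1.c below". They are capped: "Weights greater than the 95th percentile of weights will be set to the 95th percentile weight". In this section, multiple imputation is for missing covariates.

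SAP 3.1.c supplies a single list for both models: "The linear weighted GEE model for PDC and the logistic model for propensity of observation will each contain terms for randomization stratification variables", followed by calendar month of randomization, arm, follow-up month, arm by month, demographics and comorbidities. No baseline, lagged or cumulative PDC appears, and no gap or refill history.

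SAP 3.1.a (Treatment comparisons) builds the 12-month contrast from the monthly parameters, "which incorporate the adjustments for early termination of some subjects using the weighted GEE approach".

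**The concern.** Loss that depends on PDC already observed is a standard case of MAR that is not MCAR. Weights correct for it only if the observation model contains that history. An independence working covariance cannot supply it either, because it does not use a patient's earlier values to inform later months. With one shared list, the weights address only loss explained by covariates that the mean model already adjusts for.

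The report would then describe the primary contrasts as adjusted for MAR early termination, although loss following observed low adherence is not adjusted for. If such loss were more common among texted patients, their later months would over-represent good adherers and the comparison with usual care would lean towards the texts.

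**Working it through.** **1. Plan figures used for scale.** SAP 3.1.f gives an SD of 0.22 (mean 0.732), a 10-point difference, two-sided level 0.05/6 and 80% power. The normal approximation is n = 2 × (2.638 + 0.842)² × 0.22² / 0.10² = 117.2, so 118. The t-test version gives 119, as the SAP states. The point does not depend on this figure; it confirms the SD.

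**2. Standard error at achieved size.** Enrolment is 1,235 + 7,266 + 1,000 = 9,501, or about 2,375 per arm. SE = 0.22 × √(2/2375) = 0.00638, or 0.64 percentage point. The stage 1 level is 0.05/3 = 1.67%, with critical value 2.394.

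**3. Simulation calibrated to the SAP.** Twelve monthly PDC values in [0,1] had a patient effect, serial correlation, an early rise and 0.5% intermittent inpatient months. Systems were in the enrolled proportions; mean 0.735, SD of 12-month PDC 0.221. There was no true effect. There were 20,000 patients per arm and 6 replicates; Monte Carlo error was 0.02 point or less. All loss rates are assumptions. Monthly loss hazards are shown for previous PDC at least 0.5 / below 0.5. Entries are bias in texted minus control, in points; the revised weights add PDC history by arm.

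| Assumed loss | Unweighted | SAP weights, capped | Revised, uncapped | Revised, capped |
|---|---|---|---|---|
| STOP route: texted only, 1%/3%, earliest 10% of patients | 0.05 | 0.05 | 0.00 | 0.02 |
| Same, earliest 20% | 0.10 | 0.10 | 0.01 | 0.03 |
| Both arms 1%/3% | 0.02 | 0.02 | 0.04 | 0.03 |
| Illustration: texted 1%/3%, control 0.8%/2.4% | 0.13 | 0.13 | 0.04 | 0.11 |
| Illustration: texted only 0.5%/1.5% | 0.30 | 0.30 | 0.02 | 0.10 |
| Illustration: texted only 1%/3% | 0.57 | 0.57 | 0.02 | 0.21 |
| Illustration: texted 1%/3%, control 1.3%/1.3% | 0.60 | 0.60 | 0.04 | 0.21 |

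Hazards of 1%/3% lose 14.8% of those exposed, so the STOP rows lose 0.10 × 14.8% = 1.5% and 0.20 × 14.8% = 3.0% of the texted arm.

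**4. Effect on stage 1 error.** With bias b, error = P(Z > 2.394 − b/0.638) + P(Z < −2.394 − b/0.638). For b = 0, 0.10, 0.30 and 0.60 point this is 1.7%, 1.8%, 2.9% and 7.3%. At 2,375 per arm (400 replicates, Monte Carlo error 0.7), rejection on the STOP route (earliest 20%) was 2.0% with SAP weights and 2.2% with revised weights, so no improvement is visible. In the texted-only 1%/3% illustration it was 6.8% and 1.5%.

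**5. Second simulation, previous-month PDC only.** Two arms had 4,750 patients in total, with a true difference of 3 points and 60 replicates. With loss unrelated to PDC, all methods gave 3.04 to 3.05 (full data 3.03). With equal dependence in both arms and 22% of months missing, the difference was 2.94 unweighted, 2.94 with SAP weights and 3.04 with lagged-PDC weights (full data 3.04). The control mean was 1.94 points too high under both the unweighted and SAP analyses. With dependence in the active arm only, SAP weights gave 4.74, uncapped lagged-PDC weights 2.96 and capped ones 3.45 (full data 2.96). These strong mechanisms show how the methods behave; they are not estimates for this trial.

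**6. What the SAP weights do achieve.** When the mean model was misspecified and loss depended on a listed covariate, they cut the bias in the control mean from 0.33 to 0.12 point. In a further check, the effect was assumed to be 5 points at Denver Health and 2 elsewhere, with half of VA and UCHealth truncated. SAP weights were then within 0.01 point of target. Lagged weights that left truncation out were off by 0.15 to 0.18. With a system-by-month factor the bias was −0.02 to 0.01.

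**The case against.** The strongest reply is that the documented exposure is tiny. Under the protocol's plan for responding to text messages, full data loss after STOP applied to the original consent cohort, those patients are telephoned for permission to continue, and later STOP replies end messages only. The SAP says "while this was fixed early in the study a small percentage of early patients have shorter PDC observation". The resulting bias is well inside the standard error, and correcting it changed nothing visible at trial size. This stands and limits the severity.

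The SAP also plans a check: "We will carry out the recommended sensitivity analyses to the MAR assumption using methods based on pattern mixture models and imputation". SAP 3.1.d adds a repeat limited to medications with a later fill. These probe robustness, but they leave the primary estimate as it is.

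Third, provider cancellation and death may not be missing data at all. The protocol's Ascertainment of Outcomes counts at-risk days only while a medication is prescribed and excludes days after death, whereas SAP 3.1.a lists both as early termination. If those months lie outside the estimand, essentially only the STOP route remains among the documented arm-specific causes. That is fair, and the plan needs to settle it first.

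A reader might infer that the weighting is useless. It is not: step 6 shows that it can matter for the VA and UCHealth truncation, in systems holding 2,235 of 9,501 patients. A reader might also infer an arm-specific route through cancellation, because only texted patients can reply DONE to report one. SAP 3.1.b takes cancellations from the health record, and the documents do not say that replies feed the PDC calculation.

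**Conclusion.** The concern holds as a mismatch between the stated assumption and the specification. As written, the weighted analysis is valid only when loss is independent of PDC given the 3.1.c covariates, which is narrower than the MAR the SAP invokes.

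Material bias in the arm contrast needs a relation between loss and PDC that differs by arm. For the documented STOP route it is about 0.05 to 0.10 point, under assumed hazards and an assumed early cohort of 10 to 20% of patients. With equal dependence it is essentially none (0.02 point in the calibrated simulation; about 0.1 point in the second, at 22% missing months), although the arm means can shift. The range 0.13 to 0.60 point is illustration only. Even 0.60 is 6% of the 10-point planning difference, though at this sample size it would raise stage 1 error to 7.3%.

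A reader might conclude that the primary contrasts are materially biased. The documents give neither loss by arm nor any link between loss and PDC, so they do not support that. Severity is minor to moderate.

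**What to change.** In SAP 3.1.a and 3.1.c:

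1. State whether months after death or medication cancellation lie outside the estimand, reconcile this with the protocol's at-risk-day definition, and weight only for loss inside it.
2. For that non-administrative loss, fit a month-by-month observation model among patients still followed, with the 3.1.c terms plus previous-month PDC and its interaction with arm. Put these extra terms in the observation model only, not in the mean model, and multiply the conditional probabilities.
3. Keep the VA and UCHealth truncation in the weights as a separate factor, system by follow-up month, without PDC history.
4. Report the primary contrast with and without the 95th-percentile cap. The cap removes part of the correction: in the table it leaves 0.21 of 0.57 point. With an early-cohort term in the model it left 0.09 of the 0.10 point on the STOP route, because under 5% of observations carry the large weights.

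If the sponsor keeps the current weights as primary, the SAP should state that MAR is conditional on the 3.1.c covariates only and report the lagged-PDC weights as a sensitivity analysis.

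The cost is SAP wording, somewhat more code and a small loss of precision. The simulated SE rose from 0.636 to 0.637 point on the STOP route, from 0.638 to 0.647 at 14.8% loss, and from 0.658 to 0.680 (about 3%) when the truncation was weighted as well.

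### The primary 12-month PDC comparison is defined as a sum of 12 monthly parameters with no divisor, which is not on the PDC scale, although an average is evidently intended

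*Combined protocol and SAP*

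**What the plan says.** The revised SAP replaces the daily logistic model with a longitudinal one. Under Longitudinal models and GEE (3.1.a) it states that "we will use a longitudinal model with PDC calculated for monthly intervals", fitted by weighted GEE with an identity link. Section 3.1.b gives the ratio: "In general, PDC is the sum of observation days covered divided by the sum of observation days". It then places that ratio inside each month: "For the longitudinal analyses planned, these definitions will be applied within each longitudinal interval". Section 3.1.c puts treatment arm, follow-up month and their interaction in the model, without stating the coding.

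Under Treatment comparisons (3.1.a), the parameter estimates are to be used "to construct expected PDC treatment differences". The next sentence gives the calculation: "The estimand comparisons will be 12-month PDC, calculated by summing the 12 monthly longitudinal parameters". No divisor or weights follow there or elsewhere. The comparisons cover each active arm against control and then, in stage 2, "the three pairwise comparisons among active intervention arms are tested with the Holm method".

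The power section (3.1.f) plans on this effect: "Difference between treatments in PDC of 10 percentage points".

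**The concern.** With an identity link, each monthly parameter is a proportion or a difference in proportions. The denominator in the PDC ratio is used up within the month, so it does not rescale a sum across months. Taken as written, the rule gives a quantity that runs from 0 to 12 for an arm and from -12 to 12 for a difference. That is not the PDC difference that the SAP says clinicians asked for.

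The sentence also leaves open which 12 parameters are meant. The natural reading is the 12 month-specific differences between two arms. However, in a reference-coded model each active arm also has exactly 12 coefficients (one main effect and 11 interactions), and adding those gives something else.

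At stake are the size and interval of the primary result, in the one sentence that defines it.

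**Working it through.** **Inputs.** From 3.1.f: planning difference 0.10, SD 0.22, mean 0.732, power 80%, two-sided level 0.05/6, stated n = 119 per arm. From 3.1.a: monthly PDC, bounded by 0 and 1, identity link, sum of 12 parameters. From 3.1.c: arm, month and arm-by-month terms.

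**1. The plan's own figure.** Normal approximation: n = 2(2.638 + 0.842)² × 0.22² / 0.10² = 117.2, so 118. The two-sample t calculation gives 118.97, so 119 per arm and 4 × 119 = 476 in total, as stated. The planning difference and SD are therefore on the 0-1 scale of a 12-month PDC. On the summed scale both grow by 12 (1.20 and 2.64). The ratio stays at 0.10/0.22 = 1.20/2.64 = 0.4545, so the sample size is unaffected.

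**2. Sum against average, month-specific differences.** Let D₁, …, D₁₂ be the monthly differences between two arms, with robust covariance V.
- Sum: S = ΣDₘ, with SE(S) = √(1′V1).
- Average: A = S/12, with SE(A) = √(1′V1)/12.
- So S/SE(S) = A/SE(A), and z and p are identical.

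With the plan's values held constant over months, 12 × 0.10 = 1.20, against a maximum possible PDC difference of 1. An arm level of 0.732 becomes 12 × 0.732 = 8.78.

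**3. Numerical check.** The data were simulated with assumed values: 1,500 patients per arm and monthly effects falling linearly from 0.05 to 0.01.

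| | Estimate | SE | 95% CI | z | p |
|---|---|---|---|---|---|
| Sum | 0.412 | 0.0798 | 0.256 to 0.569 | 5.17 | 2.4 × 10⁻⁷ |
| Average | 0.0344 | 0.00665 | 0.0213 to 0.0474 | 5.17 | 2.4 × 10⁻⁷ |

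The estimate, SE and limits differ by a factor of 12. The test does not differ.

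**4. Raw reference-coded coefficients.** With control and month 1 as reference, the arm main effect is β = D₁ and the interactions are γₘ = Dₘ − D₁ for m = 2 to 12. Adding them gives β + Σγₘ = ΣDₘ − 11D₁. For the assumed true effects (0.05 falling to 0.01, ΣDₘ = 0.36), this is 0.36 − 0.55 = −0.19, against a true average of 0.36/12 = 0.03. The sign is wrong, the result is not a fixed multiple of the average, and the test changes as well. The correct combination is β + (1/12)Σγₘ, which equals A.

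**5. Choice of weights.** Take, as an assumption, eleven 30-day intervals and one of 35 days (365 in all). For the same effects, the day-weighted average is 0.0297 and the equal-month average is 0.0300. The sum is 0.36/0.0297 = 12.1 times the former and exactly 12 times the latter.

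**The case against.** The strongest reply is that this is shorthand. The sentence before it speaks of PDC differences, PDC is described as bounded by 0 and 1, 3.1.b defines it as a ratio, and 3.1.f plans in percentage points. The SAP also uses the word sum loosely elsewhere. Section 3.1.b describes PDC-C1, which is a ratio, as a sum of medication-specific values weighted by the share of the 365 days observed. For two fully observed medications those weights total 2. Much of this stands: an average is evidently intended. But these places establish the intention only. They contradict the calculation sentence and do not supply its divisor.

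It is also fair to say that contrast coefficients can sit in the programming specifications, so writing out all six in the SAP is optional. Equal monthly weights are not the only defensible choice either, because PDC-C1 gives each day on each medication equal weight.

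A reader might infer that modest effects will be published 12 times too large without anyone noticing, since any true difference below 1/12 (8.3 points) gives a sum below 1. The documents do not support that. It would require analysts to ignore the stated PDC-difference scale and to compare the result with no arm-level value, where a figure such as 8.78 is plainly impossible.

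**Conclusion.** The rule is wrong as written and should be fixed. On the natural reading (12 month-specific differences, equal-month average as target) the scale factor is exactly 12 for the estimate, SE and confidence limits, and it is close to 12 against a day-weighted average.

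A reader might infer that the primary tests or the gatekeeping are invalid. On the natural reading they are not: z, p-values, gatekeeping decisions and sample size are all unchanged. The opposite inference, that the tests are safe whatever is summed, is also too strong. If raw reference-coded coefficients were added, the estimate and the test would both be wrong, and the SAP does not state the coding that would rule this out. That is a possible misreading rather than a likely one.

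The practical risk is therefore a mis-scaled primary estimate and interval, not a changed decision. The factor follows from the SAP's own definitions. The simulated effects, arm size and interval lengths above are assumptions used only to illustrate it.

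**What to change.** In SAP 3.1.a, Treatment comparisons, replace summing with averaging, for example: *The estimand is the difference between arms in 12-month PDC, calculated as the weighted average of the 12 model-based month-specific differences between arms, with weights that sum to 1. The standard error and confidence interval come from the same linear contrast of the robust covariance matrix.*

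State which weights are primary: 1/12 for each month, or proportional to the days in each interval. The two should differ only slightly.

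Add a note that raw reference-coded coefficients must not simply be added. With equal weights and control as reference, an active-versus-control contrast has coefficient 1 on that arm's main effect and 1/12 on each of its 11 interactions. An active-versus-active contrast is the difference of two such contrasts. The six contrasts may be listed in the SAP or in the programming specifications.

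The cost is one sentence, one note and the matching contrast statements. The data, model, sample size and gatekeeping procedure stay as they are.
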